8.3.3 Visit 3 (Day 8)

There is no CAE® evaluation at Day 8, Visit 3.

- Study Drug Diary/Study Drug Collection. Site staff must confirm that subjects have NOT administered their morning study drug dose at home. Subjects will undergo repeat assessments as follows.
- Monitoring and Query AEs
- Recording of all Changes in Concomitant Medications
- Ora Calibra® Ocular Discomfort Scale
- Ora Calibra® Ocular Discomfort and 4-Symptom Questionnaire
- VAS discomfort scale
- OSDI
- BCVA Utilizing an ETDRS Chart
- Slit Lamp Biomicroscopy
- Conjunctival redness
- TFBUT
- Fluorescein Staining
- Lissamine Green Staining
- Study Drug Instillation at the Study Site Subjects will self-administer their first study drug dose bilaterally for Day 8 at the study site following the last study assessment. The evening dose will be administered at home, by the subject.
- Monitoring and Query AEs
- Study Drug Re-Dispensation. Prior to discharge from the study site on Visit 3 (Day 8), study drug kits from Day 1 will be re-dispensed to subjects with the remaining study drug to complete up to Day 15. Subjects will again be educated in study drug diary recording and self-administration of study drug. Subjects will be instructed to NOT self-administer study drug on the morning of their next scheduled study visit (Visit 4, Day 15).
- Schedule Next Visit Subjects will be scheduled for Visit 4.

8.3.4 Visit 4: Day 15 ± 2

Pre-CAE®

- Study Drug Diary/Study Drug Collection Subject study drug diaries and all used/unused study drug vials dispensed for Days 8 to 15 should be collected and reviewed by a trained study technician.
- Site staff must confirm subjects have NOT administered their morning study drug dose at home
- Monitor and Query AEs
- Record all Changes in Concomitant Medications
- Ora Calibra® Ocular Discomfort Scale
- Ora Calibra® Ocular Discomfort and 4-Symptom Questionnaire
- VAS discomfort scale
- OSDI
- BCVA Utilizing an ETDRS Chart
- Slit Lamp Biomicroscopy
- Conjunctival redness
- TFBUT
- Fluorescein Staining
- Lissamine Green Staining

CAE®

- During the CAE® exposure, ODS will be collected at [REDACTED].

Post-CAE®

- Ora Calibra® Ocular Discomfort Scale
- Ora Calibra® Ocular Discomfort and 4-Symptom Questionnaire Ocular Discomfort Score
- VAS discomfort scale
- Slit lamp biomicroscopy
- Conjunctival redness
- TFBUT
- Fluorescein Staining
- Lissamine Green Staining

- Schirmer's test
- Blood sampling for Immunogenicity testing
- Study Drug Diary/Study Drug Dispensation Prior to discharge from the study site on Visit 4 (Day 15), subjects will be educated in study drug diary recording and self-administration of study drug. Subjects will receive their assigned study drug kit with sufficient supply to last until Visit 5 and will be instructed to NOT self-administer study drug on the morning of their next scheduled study visit (Visit 5, Day 29).
- Schedule Next Visit Subjects will be scheduled for Visit 5.

8.3.5 Visit 5: Day 29 ± 2

Pre-CAE®

- Study Drug Diary/Study Drug Collection Subject study drug diaries and all used/unused study drug vials dispensed for Days 15 to 29 should be collected and reviewed by a trained study technician.
- Site staff must confirm subjects have NOT administered their morning study drug dose at home
- Monitoring and Query of AEs
- Record all Changes in Concomitant Medications
- Ora Calibra® Ocular Discomfort Scale
- Ora Calibra® Ocular Discomfort and 4-Symptom Questionnaire
- VAS discomfort scale
- OSDI
- BCVA Utilizing an ETDRS Chart
- Slit Lamp Biomicroscopy
- Conjunctival redness
- TFBUT
- Fluorescein Staining
- Lissamine Green Staining

CAE®

- During the CAE® exposure, ODS will be collected at [REDACTED]
[REDACTED].

Post-CAE®

- Ora Calibra® Ocular Discomfort Scale

- Ora Calibra® Ocular Discomfort and 4-Symptom Questionnaire Ocular Discomfort Score
- VAS discomfort scale
- Slit lamp biomicroscopy
- Conjunctival redness
- TFBUT
- Fluorescein Staining
- Lissamine Green Staining
- Schirmer's test
- Blood sampling for Immunogenicity testing
- Monitoring and Query of AEs
- Study Drug Diary/Study Drug Dispensation Prior to discharge from the study site on Visit 5 (Day 29), subjects will be educated in study drug diary recording and self-administration of study drug. Subjects will receive their assigned study drug kit with sufficient supply to last until Visit 6 and will be instructed to NOT self-administer study drug on the morning of their next scheduled study visit (Visit 6, Day 57).
- Schedule Next Visit Subjects will be scheduled for Visit 6.

8.3.6 Visit 6: Day 57 ± 3

Pre-CAE®

- Study Drug Diary/Study Drug Collection Subject study drug diaries and all used/unused study drug vials dispensed for Days 29 to 57 should be collected and reviewed by a trained study technician.
- Site staff must confirm subjects have NOT administered their morning study drug dose at home
- Monitoring and Query of AEs
- Record all Changes in Concomitant Medications
- Urine Pregnancy Test (for females of childbearing potential)
- Ora Calibra® Ocular Discomfort Scale
- Ora Calibra® Ocular Discomfort and 4-Symptom Questionnaire
- VAS discomfort scale
- OSDI
- BCVA Utilizing an ETDRS Chart
- Slit Lamp Biomicroscopy

- Conjunctival redness
- Tear sample collection from both eyes
- TFBUT
- Fluorescein Staining
- Lissamine Green Staining

CAE®

- During the CAE® exposure, ODS will be collected at [REDACTED] s.

Post-CAE®

- Ora Calibra® Ocular Discomfort Scale
- Ora Calibra® Ocular Discomfort and 4-Symptom Questionnaire Ocular Discomfort Score
- VAS discomfort scale
- Slit lamp biomicroscopy
- Conjunctival redness
- TFBUT
- Fluorescein Staining
- Lissamine Green Staining
- Schirmer's test
- Intraocular Pressure
- Dilated fundoscopy
- Blood sampling for Immunogenicity testing
- Monitoring and Query of AEs
- Study Exit

8.4 SCHEDULE OF VISITS, MEASUREMENTS AND DOSING

8.4.1 Scheduled Visits

Refer to [Appendix 1](#) for a schedule of visits and measurements.

8.4.2 Unscheduled Visits

These visits may be performed in order to ensure subject safety. All procedures performed at an unscheduled visit will be recorded in the source documents and on the

Unscheduled Visit eCRF pages. Any procedure indicated in the eCRF that is not performed should be indicated as “Not done.”

Evaluations that may be conducted at an Unscheduled Visit include:

- Slit-lamp Biomicroscopy;
- Visual Acuity;
- Intraocular Pressure;
- Urine Pregnancy Test;
- Dilated Fundoscopy;
- Assessment of Adverse Events;
- Assessment of concomitant medications and/or treatments; and
- Any other assessments needed in the judgment of the investigator.

8.5 COMPLIANCE WITH PROTOCOL

Subjects will be instructed on proper use of the subject daily diary and proper instillation and storage of study drug at the end of Visits 1, 2, 3, 4 and 5, and given written instructions. The subject daily diaries and used and unused study drug vials will be collected at each visit from Visit 2 up to and including Visit 6 to assess dosing and symptom assessment compliance. Dosing compliance will be based off of the used and unused vial count. If the subject is less than 80% or more than 125% compliant with dosing based on the expected number of used vials, then the subject will be deemed non-compliant and a deviation should be recorded.

In the subject daily diary, if more than 20% of Dose Taken boxes are checked “no”, left blank, or missing for a diary period, a subject will be deemed non-compliant and a diary deviation will be recorded. If more than 20% of the total diary symptom assessments for that dosing period are missed, these subjects will be deemed non-compliant and a diary symptom assessment deviation will be recorded. These guidelines will be used by the Investigator for determining the subject’s necessary compliance for the study and for recording deviations from this compliance.

8.6 SUBJECT DISPOSITION

8.6.1 Completed Subjects

A completed subject is one who has not been discontinued from the study.

8.6.2 Discontinued Subjects

Subjects may be discontinued prior to their completion of the study due to:

- AEs;
- unmasking when medically necessary;
- protocol violations;
- administrative reasons (e.g., inability to continue, lost to follow up);
- sponsor termination of study;
- subject choice (e.g. withdrawal of consent); and
- other

Note: In addition, any subject may be discontinued for any sound medical reason at the discretion of the investigator.

Notification of a subject discontinuation and the reason for discontinuation will be made to Ora and/or study sponsor and will be clearly documented on the eCRF.

Discontinued subjects will not be replaced.

8.7 STUDY TERMINATION

The study may be stopped at any time by the investigator, the sponsor, and/or Ora with appropriate notification.

8.8 STUDY DURATION

An individual subject's participation will involve 6 visits over approximately a 10-week (~70 days) period (56 days of treatment and 14 days pre-screening).

8.9 MONITORING AND QUALITY ASSURANCE

During the course of the study a monitor, or designee, will make routine site visits to review protocol compliance, assess study drug/device accountability, and ensure the study is being conducted according to the pertinent regulatory requirements. The review of the subjects' medical records will be performed in a manner that adequately maintains subject confidentiality. Further details of the study monitoring will be outlined in a monitoring plan.

Regulatory authorities of domestic and foreign agencies, quality assurance and or its designees may carry out on-site inspections and/or audits which may include source data checks. Therefore direct access to the original source data will be required for inspections and/or audits. All inspections and audits will be carried out giving consideration to data protection as well as subject confidentiality to the extent that local, state, and federal laws apply.

9 ADVERSE EVENTS

An AE is defined as any untoward medical occurrence associated with the use of an investigational product (IP) in humans, whether or not considered IP-related. An AE can be any unfavorable and unintended sign (eg, an abnormal laboratory finding), symptom, or disease temporally associated with the use of an IP, without any judgment about causality. An AE can arise from any use of the IP (eg, off-label use, use in combination with another drug or medical device) and from any route of administration, formulation, or dose, including an overdose. An AE can arise from any delivery, implantation, or use of a medical device, including medical device failure, subject characteristics that may impact medical device performance (eg, anatomical limitations), and therapeutic parameters (eg, energy applied, sizing, dose release) associated with medical device.

All AEs spontaneously reported by the subject and/or in response to an open question from study personnel or revealed by observation, physical examination or other diagnostic procedures will be recorded in the source document and on the appropriate pages of the CRF. Any clinically relevant deterioration in clinical finding is considered an AE and must be recorded. When possible, signs and symptoms indicating a common underlying pathology should be noted as 1 comprehensive event.

Documentation regarding the AE should be made as to the nature, date of onset, end date, severity, relationship to IP, action(s) taken, seriousness, and outcome of any sign or symptom observed by the physician or reported by the subject upon indirect questioning.

9.1.1 Severity

Severity of an AE is defined as a qualitative assessment of the degree of intensity of an AE as determined by the investigator or reported to him/her by the subject. The assessment of severity is made irrespective of relationship to IP or seriousness of the event and should be evaluated according to the following scale:

- *Mild*: Event is noticeable to the subject, but is easily tolerated and does not interfere with the subject's daily activities.
- *Moderate*: Event is bothersome, possibly requiring additional therapy, and may interfere with the subject's daily activities.
- *Severe*: Event is intolerable, necessitates additional therapy or alteration of therapy, and interferes with the subject's daily activities.

9.1.2 Relationship to Investigational Product

The relationship of each AE to the IP should be determined by the investigator using these explanations:

- **Suspected:** A reasonable possibility exists that the IP caused the AE. A suspected AE can be further defined as:
 - *Definite:* Relationship exists when the AE follows a reasonable sequence from the time of IP administration, follows a known response pattern of the drug class, is confirmed by improvement on stopping the IP and no other reasonable cause exists.
 - *Probable:* Relationship exists when the AE follows a reasonable sequence from the time of IP administration, follows a known response pattern of the drug class, is confirmed by improvement on stopping the IP and the suspect IP is the most likely of all causes.
 - *Possible:* Relationship exists when the AE follows a reasonable sequence from the time of administration, but could also have been produced by the subject's clinical state or by other drugs administered to the subject.
- **Not Suspected:** A reasonable possibility does not exist that the IP caused the AE. A not suspected AE can further be defined as:
 - *Not Related:* Concurrent illness, concurrent medication, or other known cause is clearly responsible for the AE, the administration of the IP and the occurrence of the AE are not reasonably related in time, OR exposure to IP has not occurred.

Types of evidence that would suggest a causal relationship between the IP and the AE include: a single occurrence of an event that is uncommon and known to be strongly associated with IP exposure (eg, angioedema, hepatic injury, Stevens-Johnson Syndrome); one or more occurrences of an event that is not commonly associated with IP exposure, but is otherwise uncommon in the population exposed to the IP (eg, tendon rupture); an aggregate analysis of specific events observed in a clinical trial (such as known consequences of the underlying disease or condition under investigation or other events that commonly occur in the study population independent of drug therapy) that indicates those events occur more frequently in the IP-treatment group than in a concurrent or historical control group.

9.1.3 Expectedness

The expectedness of an AE should be determined based upon existing safety information about the IP using these explanations:

- *Unexpected:* an AE that is not listed in the Investigator's Brochure (IB) or Report of Prior Investigations (ROPI) or is not listed at the specificity or severity that has been observed.
- *Expected:* an AE that is listed in the IB or ROPI at the specificity and severity that has been observed.

- *Not applicable*: an AE unrelated to the IP.

AEs that are mentioned in the IB or ROPI as occurring with a class of products or as anticipated from the pharmacological/ mechanical (or other) properties of the product, but are not specifically mentioned as occurring with the particular product under investigation are to be considered unexpected.

The investigator should initially classify the expectedness of an AE, but the final classification is subject to the Medical Monitor's determination.

9.2 SERIOUS ADVERSE EVENTS

An AE is considered serious if, in the view of either the investigator or sponsor, it results in any of the following outcomes:

- Death;
- A life-threatening AE;

Note: An AE is considered "life-threatening" if, in the view of either the investigator or sponsor, its occurrence places the subject at immediate risk of death. It does not include an AE that, had it occurred in a more severe form, might have caused death.

- Inpatient hospitalization or prolongation of existing hospitalization;

Note: The term "inpatient hospitalization" refers to any inpatient admission (even if less than 24 hours). For chronic or long-term inpatients, inpatient admission includes transfer within the hospital to an acute/intensive care inpatient unit. Inpatient hospitalization does not include: emergency room visits; outpatient/same-day/ambulatory procedures; observation/short stay units; rehabilitation facilities; hospice facilities; nursing homes; or clinical research/phase 1 units.

Note: The term "prolongation of existing hospitalization" refers to any extension of an inpatient hospitalization beyond the stay anticipated or required for the reason for the initial admission as determined by the investigator or treating physician.

- A persistent or significant incapacity or substantial disruption of the ability to conduct normal life functions;

Note: A serious adverse event (SAE) specifically related to visual threat would be interpreted as any potential impairment or damage to the subject's eyes (eg, hemorrhage, retinal detachment, central corneal ulcer or damage to the optic nerve).

- A congenital anomaly/birth defect.

Important medical events that may not result in death, are life-threatening, or require hospitalization may be considered serious when, based upon appropriate medical judgment, they may jeopardize the subject and may require medical or surgical intervention to prevent one of the outcomes listed in this definition.

9.3 PROCEDURES FOR REPORTING ADVERSE EVENTS

All adverse events and their outcomes must be reported to Ora, the study sponsor, and the IRB/IEC as required by the IRB/IEC, federal, state, or local regulations and governing health authorities and recorded on the appropriate eCRF.

9.3.1 Reporting a Suspected Unexpected Adverse Reaction

All adverse events that are ‘suspected’ and ‘unexpected’ are to be reported to Ora, the study sponsor and the IRB/IEC as required by the IRB/IEC, federal, state, or local regulations and governing health authorities.

9.3.2 Reporting a Serious Adverse Event

To ensure subject safety, all serious adverse events, regardless of relationship to the study drug, must be immediately reported. All information relevant to the serious adverse event must be recorded on the appropriate case report forms. The investigator is obligated to pursue and obtain information requested by Ora and/or the sponsor in addition to that information reported on the case report form. All subjects experiencing a serious adverse event must be followed up and the outcome reported.

In the event of a serious adverse event, the investigator must notify Ora and the sponsor immediately; obtain and maintain in his/her files all pertinent medical records, information, and medical judgments from colleagues who assisted in the treatment and follow-up of the subject; provide Ora and the study sponsor with a complete case history, which includes a statement as to whether the event was or was not suspected to be related to the use of the study drug; and inform the IRB of the adverse event within their guidelines for reporting serious adverse events.

Contact information for reporting Serious Adverse Events:

Name:	[REDACTED]
Title:	Clinical Project Manager, Dry Eye
Company:	Ora, Inc.
Office Telephone:	[REDACTED]
Alternative Telephone:	[REDACTED]
Office Facsimile:	[REDACTED]

Name:	[REDACTED]
Title:	Medical Monitor
Office Telephone:	[REDACTED]
Mobile Phone:	[REDACTED]
Office Facsimile:	[REDACTED]

9.4 PROCEDURES FOR UNMASKING (IF APPLICABLE)

All subjects, investigators, and study personnel involved with the conduct of the study will be masked with regard to treatment assignments. When medically necessary, the investigator may need to determine what treatment arm has been assigned to a subject. When possible (i.e., in non-emergent situations), Ora and/or the study sponsor should be notified before unmasking study drug. The unmasked subject will be discontinued from the study.

9.5 TYPE AND DURATION OF THE FOLLOW-UP OF SUBJECTS AFTER ADVERSE EVENTS

The investigator will follow unresolved AEs to resolution until the subject is lost to follow-up or until the AE is otherwise classified. Resolution means the subject has returned to baseline state of health or the Investigator does not expect any further improvement or worsening of the AE. If the patient is lost to follow-up, the Investigator should make 3 reasonable attempts to contact the patient via telephone, post, or certified mail. All follow-up will be documented in the subject's source document. Non-serious AEs identified on the last scheduled contact must be recorded on the AE eCRF with the status noted.

If the Investigator becomes aware of any new information regarding an existing SAE (i.e., resolution, change in condition, or new treatment), a new SAE/Unanticipated Report Form must be completed and faxed to Ora within 24 hours of the site's awareness of the new information. The original SAE form is not to be altered. The report should describe whether the event has resolved or continues and how the event was treated.

10 STATISTICAL HYPOTHESES AND METHODS OF ANALYSES

10.1 ANALYSIS POPULATIONS

The following analysis populations will be considered:

- Intent-to-Treat Population – The intent-to-treat (ITT) population includes all randomized subjects. The primary analysis will be performed on the ITT population with the Last Observation Carried Forward (LOCF) imputation method for missing values. The ITT population may also be analyzed with observed data only (i.e.,

without LOCF) and using multiple imputation methods to assess sensitivity. Subjects in the ITT population will be analyzed as randomized.

- Per Protocol Population – The per protocol (PP) population includes subjects in the ITT population who do not have significant protocol deviations and who complete the study. Protocol deviations will be assessed prior to database lock and unmasking. The PP population will be analyzed using observed data only for efficacy variables. Subjects in the PP population will be analyzed as treated.
- Safety Population – The safety population includes all randomized subjects who have received at least one dose of the investigational product. The safety population will be analyzed for all safety assessments. Subjects in the Safety population will be analyzed as treated.

The statistical analysis of safety data will be performed for the safety population. The analysis of baseline and efficacy data will be performed for the ITT population. The primary efficacy analysis will also be performed on the PP population as sensitivity analyses.

10.2 STATISTICAL HYPOTHESES

The statistical hypotheses are stated in terms of one-sided hypotheses, although statistical testing will be two-sided.

H_{01} : There is no difference between HL036 ophthalmic solution (0.25% or 0.10%) and placebo in the change from baseline of the pre-CAE® inferior corneal fluorescein staining at Day 57 (Visit 6), using the Ora Calibra® scale.

H_{11} : The change from baseline of the pre-CAE® inferior corneal fluorescein staining at Day 57 (Visit 6) using the Ora Calibra® scale is less with HL036 ophthalmic solution (0.25% or 0.10%) than with placebo.

H_{02} : There is no difference between HL036 ophthalmic solution (0.25% or 0.10%) and placebo in the change from baseline of the pre-CAE® ocular discomfort evaluated at Visit 6, using the Ora Calibra® Ocular Discomfort Scale.

H_{12} : The change from baseline of the pre-CAE® ocular dryness at Visit 6 using the Ora Calibra® Ocular Discomfort Scale is less with HL036 ophthalmic solution (0.25% or 0.10%) than with placebo.

10.3 SAMPLE SIZE

The primary objective of the study is to demonstrate a statistically significant difference between the active treatments and placebo.

This study is expected to enroll 50 subjects in each of the three treatment arms, for a total of 150 randomized subjects. Assuming a 10% drop out rate, 45 subjects per group are expected to complete the study.

Assuming a common standard deviation in the change from baseline for the pre-CAE® inferior corneal fluorescein staining of 0.72 units, a sample size of 45 subjects per group will have 90% power to detect a difference of 0.5 units between each of the active treatment groups and the placebo group using a two-sample t-test at a significance level of 0.05. A sample size of 45 subjects per treatment arm will have 90% power to detect a mean difference of 0.80 units in the change from baseline for the pre-CAE® ocular discomfort as assessed by the Ora Calibra® Ocular Discomfort Scale, assuming a standard deviation of 1.15 units. Using an analysis of covariance model (ANCOVA) for each primary endpoint should yield standard deviations no greater than those from a two-sample t-test. Therefore, the power for each endpoint for both the sign and the symptom is 81%, assuming independence between the endpoints. The power for both the sign and the symptom in both active treatments is 66%, assuming independence of treatments.

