5 STUDY POPULATION

5.1 NUMBER OF SUBJECTS

It is estimated that approximately 375 subjects will be screened to enroll approximately 150 randomized subjects (50 in each arm). Subjects will be randomized in a 1:1:1 ratio of HL036 Ophthalmic Solution (0.25%) to HL036 Ophthalmic Solution (0.1%) to HL036 Vehicle Ophthalmic Solution.

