10.4 STATISTICAL ANALYSIS

10.4.1 General Considerations

The quantitative variables will be summarized using number of subjects (n), mean, median, standard deviation, minimum and maximum. The qualitative variables will be summarized using counts and percentages.

All summaries will be presented by treatment group. Summaries will be provided for demographics, baseline medical history, concurrent therapies, and subject disposition.

For the purpose of summarization, medical history, concurrent therapies, and adverse events will be coded to MedDRA and WHO Drug dictionaries, as appropriate.

Baseline measures are defined as the last measure prior to the initiation of study treatment, usually at Visit 2. If a measure is taken both pre-CAE® and post-CAE®, the baseline will be the time point matched value at Visit 2. For measures from daily subject diaries, baseline is defined as the average of all days during the run-in period. For changes from pre-CAE® to post-CAE® post first treatment, the change from pre-CAE® to post-CAE® at Visit 2 will be considered the baseline value.

All primary and secondary analyses will be 2-sided at a significance level of 0.05.

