10.4.4 Multiplicity Consideration

For success, significance is required for both the primary sign and the primary symptom, and for both active treatments, hence no multiplicity adjustment is necessary.

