### **9.5 Adjustments for Multiplicity**

This is a phase 2 trial that is primarily exploratory in nature. As such, to claim success for the study significance is required for both the primary sign and the primary symptom, and for both active treatments. Hence, no multiplicity adjustment is necessary.

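### The stated 66% power for success in both doses treats the two dose comparisons as independent, but they share one placebo arm; on the plan's own inputs the figure is about 70%

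*Protocol*

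**What the plan says.** The power argument in Protocol 10.3 builds up in three steps, repeated in the Protocol synopsis (Sample Size) and in SAP 6.

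- **Per comparison.** For the sign, 45 completers per arm give "90% power to detect a difference of 0.5 units between each of the active treatment groups and the placebo group", with an SD of 0.72. For the symptom, the same number gives 90% power for a difference of 0.80 with an SD of 1.15.
- **Per dose, both endpoints.** 81%, taking the two endpoints as independent.
- **Both doses, both endpoints.** "The power for both the sign and the symptom in both active treatments is 66%, assuming independence of treatments."

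The last step is the one that matches the success rule. Protocol 10.4.4 says that "significance is required for both the primary sign and the primary symptom, and for both active treatments", and SAP 9.5 repeats this. Protocol 5.1 gives the allocation: "Subjects will be randomized in a 1:1:1 ratio of HL036 Ophthalmic Solution (0.25%) to HL036 Ophthalmic Solution (0.1%) to HL036 Vehicle Ophthalmic Solution". There is one placebo arm, and it serves both dose comparisons. Neither document adjusts the 66% for this.

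**The concern.** The sentence rests on a condition that the design rules out. The three arms are independent samples, but the power statement is about two comparisons, and each of them subtracts the same placebo mean. If the placebo arm happens to do badly, both doses look better; if it does well, both look worse. The two tests therefore tend to succeed or fail together, and the probability that both succeed is higher than the product of their separate powers.

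This differs from the assumption that the sign and the symptom are independent. The documents give no sign-symptom correlation, so independence there is a planning choice and is left alone here. The correlation between the dose comparisons is not a choice: it is fixed by the allocation ratio and the common SD that the plan already assumes.

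A reader will take 66% as the planned probability of trial success under the design effects. That is what is at stake, and it is limited: the number of subjects was set by 90% power per comparison, not by this figure.

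**Working it through.** **Inputs, all from the plan**

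- Two-sided test at 0.05 (Protocol 10.4.1: "All primary and secondary analyses will be 2-sided at a significance level of 0.05").
- n = 45 per arm (Protocol 10.3: "Assuming a 10% drop out rate, 45 subjects per group are expected to complete the study").
- Sign: difference 0.5, SD 0.72. Symptom: difference 0.80, SD 1.15 (Protocol 10.3).
- Equal allocation to three arms, one of them placebo (Protocol 5.1).
- Sign and symptom independent (Protocol 10.3, kept as stated).

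**Step 1. Power per comparison.** The noncentrality of the two-sample t-test is difference / (SD × √(2/n)), with 88 degrees of freedom.

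- Sign: 0.5 / (0.72 × √(2/45)) = 3.29, power 0.9028.
- Symptom: 0.80 / (1.15 × √(2/45)) = 3.30, power 0.9038.

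The stated 90% is confirmed.

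**Step 2. The plan's own figures.**

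- One dose, both endpoints: 0.90² = 0.81, as printed.
- Both doses, both endpoints, all tests independent: 0.90⁴ = 0.656, as printed (66%). With the unrounded powers: (0.9028 × 0.9038)² = 0.666.

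**Step 3. Correlation between the dose comparisons.** Let σ be the common SD, and let A, B and P be the means of the two active arms and placebo.

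- Var(A − P) = Var(B − P) = 2σ²/n.
- Cov(A − P, B − P) = Var(P) = σ²/n.
- Correlation = (σ²/n) / (2σ²/n) = 0.5.

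**Step 4. Power with the shared placebo arm.** For one endpoint, both doses succeed with the probability that two standard normal variables with correlation 0.5 both fall below z, where z is the normal quantile of the power per comparison. For a power of 0.90, z = 1.2816. The two endpoints are then multiplied, as the plan does.

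| Power per comparison | Both doses, sign | Both doses, symptom | All four tests | If comparisons were independent | Gap |
|---|---|---|---|---|---|
| Stated 90% | 0.8324 | 0.8324 | 0.693 | 0.656 | 3.7 points |
| Exact t | 0.8368 | 0.8383 | 0.701 | 0.666 | 3.6 points (before rounding) |

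**Step 5. Check by simulation.** In 100,000 simulated three-arm trials with 45 per arm, pairwise t-tests and independent endpoints, all four tests were significant in 0.702.

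**Step 6. Sensitivity to an assumption not in the documents.** The sign and the symptom may be correlated within a subject. With the shared placebo arm kept, the power for all four tests would be:

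| Assumed endpoint correlation | From stated 90% | From exact t |
|---|---|---|
| −0.3 | 0.679 | 0.688 |
| 0 (the plan) | 0.693 | 0.701 |
| 0.2 | 0.705 | 0.713 |
| 0.4 | 0.720 | 0.728 |
| 0.6 | 0.740 | 0.747 |

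All of these values exceed the printed 66%.

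**The case against.** The strongest reply is that nothing is miscalculated. The sentence gives a conditional figure with its condition attached, and the product is correct under it. That is true, and nobody is misled about how the 66% was obtained. But stating a condition does not help when the design cannot satisfy it; the figure then describes some other trial, one with a separate placebo arm for each dose.

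A second reply is that no decision depends on it. This stands. The error is on the safe side, 45 per arm follows from the 90% per comparison, and SAP 9.5 calls the trial primarily exploratory. The point is a correction to a reported planning figure and should be given no more weight than that.

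A third reply is that 70% is itself conditional. It keeps independent endpoints, equal true effects in both doses, and t-tests on completers, whereas the primary analysis is an ANCOVA on all randomized subjects with multiple imputation. This is also true, but these are the plan's own simplifications and they underlie the 66% equally. Pooling the error variance over all three arms, as a single model would, gave 0.708 in simulation, which is still close to 70%.

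Finally, the stated 90% leads to 69.3%, and only the unrounded powers pass 70%. Describing both as about 70% is fair.

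The hypotheses in Protocol 3 and 10.2 and SAP 3.4 name the doses with an *or*. The success rule in Protocol 10.4.4 and SAP 9.5 requires both doses, and that is the event to which the 66% refers.

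**Conclusion.** The concern holds. On the plan's own inputs, the power to succeed on both endpoints in both doses is 69.3% to 70.1%, not 66%. Like for like, the understatement is 3.6 to 3.7 percentage points. The result rests on equal arms, a common SD, the planned effects in both doses and independent endpoints, all of which the plan already assumes; the correlation of 0.5 follows from the first two and needs no outside figure. The 90% and 81% statements are sound. The practical consequence is small, because the error is conservative and no design parameter depends on it, but the figure is wrong as written for this design.

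**What to change.** Replace the closing sentence of the sample size text in the Protocol synopsis, Protocol 10.3 and SAP 6 with wording such as:

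*Both doses are tested against the same placebo arm, so within each endpoint the two contrasts have a correlation of 0.5. With the two endpoints taken as independent, the probability that all four tests are significant is about 70%.*

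Delete the condition about independent treatments. Leave the 90% and 81% statements unchanged. The cost is one sentence in three places; enrolment, the significance level and the analyses do not change.
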